8.2. Discontinuation from the Study

Subjects will be discontinued in the following circumstances:

- Enrollment in any other clinical trial involving an investigational product or enrollment in any other type of medical research judged not to be scientifically or medically compatible with this study
- Participation in the study needs to be stopped for medical, safety, regulatory, or other reasons consistent with applicable laws, regulations, and good clinical practice (GCP)
- Investigator Decision
 - the investigator decides that the subject should be discontinued from the study
- Subject Decision
 - the subject requests to be withdrawn from the study

Subjects who discontinue the study early will have end-of-study procedures performed as shown in the Schedule of Activities (Section 2).

8.3. Subjects Lost to Follow-up

A subject will be considered lost to follow-up if he or she repeatedly fails to return for scheduled visits and is unable to be contacted by the study site. Site personnel are expected to make diligent attempts to contact subjects who fail to return for a scheduled visit or were otherwise unable to be followed up by the site.

9. Study Assessments and Procedures

Section 2 lists the Schedule of Activities, detailing the study procedures and their timing (including tolerance limits for timing).

[Appendix 2](#) lists the clinical laboratory tests that will be performed for this study.

[Appendix 4](#) provides a summary of the maximum number and volume of invasive samples, for all sampling, during the study.

The specifications in this protocol for the timings of safety and sample collection are given as targets to be achieved within reasonable limits. Modifications may be made to the time points based upon merging clinical information. The scheduled time points may be subject to minor alterations; however, the actual time must be correctly recorded in the eCRF. Late collection outside the stipulated time allowances or failure to obtain samples due to clinical issues, such as problems with equipment, venous access, or subject defaulting on a scheduled procedure, will not be considered as protocol deviations but the site will still be required to notify the sponsor in writing via a file-note.

Unless otherwise stated in subsections below, all samples collected for specified laboratory tests will be destroyed within 60 days of receipt of confirmed test results. Certain samples may be retained for a longer period, if necessary, to comply with applicable laws, regulations, or laboratory certification standards.

Investigators must document their review of each laboratory safety report.

9.1. Efficacy Assessments

This section is not applicable for this study.

9.2. Adverse Events

Investigators are responsible for monitoring the safety of subjects who have entered this study and for alerting Lilly or its designee to any event that seems unusual, even if this event may be considered an unanticipated benefit to the subject.

The investigator is responsible for the appropriate medical care of subjects during the study.

The investigator remains responsible for following, through an appropriate health care option, AEs that are serious or otherwise medically important, considered related to the investigational product or the study, or that caused the subject to discontinue the investigational product before completing the study. The subject should be followed until the event resolves, stabilizes with appropriate diagnostic evaluation, or is reasonably explained. The frequency of follow-up evaluations of the AE is left to the discretion of the investigator.

After the informed consent form (ICF) is signed, study site personnel will record, via eCRF, the occurrence and nature of each subject's preexisting conditions. Additionally, site personnel will record any change in the condition(s) and the occurrence and nature of any AEs.

The investigator will interpret and document whether or not an AE has a reasonable possibility of being related to study treatment, or a study procedure taking into account concomitant treatment or pathologies.

A “reasonable possibility” means that there is a cause and effect relationship between the investigational product, study device, and/or study procedure and the AE.

Planned surgeries should not be reported as AEs unless the underlying medical condition has worsened during the course of the study.

If a subject’s participation is discontinued as a result of an AE, study site personnel must report this to Lilly or its designee via eCRF.

9.2.1. Serious Adverse Events

An SAE is any AE from this study that results in one of the following:

- death
- initial or prolonged inpatient hospitalization
- a life-threatening experience (that is, immediate risk of dying)
- persistent or significant disability/incapacity
- congenital anomaly/birth defect
- important medical events that may not be immediately life-threatening or result in death or hospitalization but may jeopardize the patient or may require intervention to prevent one of the other outcomes listed in the definition above. Examples of such medical events include allergic bronchospasm requiring intensive treatment in an emergency room or at home, blood dyscrasias or convulsions that do not result in inpatient hospitalization, or the development of drug dependency or drug abuse.

Study site personnel must alert Lilly, or its designee, of any SAE within 24 hours of investigator awareness of the event via a sponsor-approved method. If alerts are issued via telephone, they are to be immediately followed with official notification on study-specific SAE forms. This 24-hour notification requirement refers to the initial SAE information and all follow-up SAE information.

Although all AEs are recorded in the eCRF after signing informed consent, SAE reporting begins after the subject has signed informed consent and has received investigational product. However, if an SAE occurs after signing informed consent, but prior to receiving investigational product, AND is considered reasonably possibly related to a study procedure then it MUST be reported.

Investigators are not obligated to actively seek AEs or SAEs in subjects once they have discontinued from and/or completed the study (the subject summary eCRF has been completed). However, if the investigator learns of any SAE, including a death, at any time after a subject has

been discharged from the study, and he/she considers the event reasonably possibly related to the study treatment or study participation, the investigator must promptly notify Lilly.

Pregnancy (maternal or paternal exposure to investigational product) does not meet the definition of an AE. However, to fulfill regulatory requirements any pregnancy should be reported following the SAE process to collect data on the outcome for both mother and fetus.

9.2.1.1. Suspected Unexpected Serious Adverse Reactions

Suspected unexpected serious adverse reactions (SUSARs) are serious events that are not listed in the IB and that the investigator identifies as related to investigational product or procedure. United States 21 CFR 312.32 and European Union Clinical Trial Directive 2001/20/EC and the associated detailed guidances or national regulatory requirements in participating countries require the reporting of SUSARs. Lilly has procedures that will be followed for the recording and expedited reporting of SUSARs that are consistent with global regulations and the associated detailed guidances.

9.2.2. Complaint Handling

Lilly collects product complaints on investigational products and drug delivery systems used in clinical trials in order to ensure the safety of study participants, monitor quality, and to facilitate process and product improvements.

Subjects should be instructed to contact the investigator as soon as possible if he or she has a complaint or problem with the investigational product so that the situation can be assessed.

- Product quality issues/complaints must be reported by site staff within 24 hours of notification to the clinical site/ study personnel, or within 24 hours of study/site personnel becoming aware of a product issue, regardless of the availability of the complaint sample.
- The investigational product should be retained under appropriate storage conditions, if available or when obtained, until instructed to return it to Lilly.
- Product complaints for Non-Lilly Products (including concomitant drugs) that do not have a Lilly Product Batch or Control number, are reported directly to the manufacturer per product label.
- The instructions outlined in the Product Complaint Form should be followed for other reporting requirements.

9.3. Treatment of Overdose

For the purposes of this study, an overdose of LY3074828 is considered any dose higher than the dose assigned through randomization.

There is no specific antidote for LY3074828. In the event of an overdose, the subject should receive appropriate supportive care and any AEs should be documented.

Refer to the IB for further details.

9.4. Safety

9.4.1. Laboratory Tests

For each subject, clinical laboratory tests detailed in [Appendix 2](#) should be conducted according to the Schedule of Activities (Section 2).

9.4.2. Vital Signs

For each subject, vital signs measurements should be conducted according to the Schedule of Activities (Section 2) and following the study-specific recommendations included in the Manual of Operations for the study. Additional vital signs may be assessed as clinically indicated as well as at the scheduled times, if warranted by the investigator.

Blood pressure and pulse rate should be measured after at least 5 minutes supine.

Unscheduled orthostatic vital signs should be assessed, where considered appropriate by the investigator.

If orthostatic measurements are required, subjects should be supine for at least 5 minutes and stand for at least 2 minutes. If the subject feels unable to stand, supine vital signs only will be recorded.

9.4.3. Electrocardiograms

For each subject, ECGs should be collected according to the Schedule of Activities (Section 2) and following the study-specific recommendations included in the Manual of Operations for the study.

Any clinically significant findings from ECGs that result in a diagnosis and that occur after the subject receives the first dose of the investigational product, should be reported to Lilly, or its designee, as an AE via eCRF.

For each subject, a single 12-lead digital ECG will be collected according to the Schedule of Activities (Section 2). Electrocardiograms must be recorded before collecting any blood for safety or PK tests. Subjects must be supine for at least 5 minutes before ECG collection and remain supine but awake during ECG collection. Electrocardiograms may be obtained at additional times, when deemed clinically necessary by the investigator. All ECGs recorded should be stored at the investigational site.

Electrocardiograms will be interpreted by a qualified physician (the investigator or qualified designee) at the site as soon after the time of ECG collection as possible, and ideally while the subject is still present, to determine whether the subject meets entry criteria at the relevant visit(s) and for immediate subject management, should any clinically relevant findings be identified.

If a clinically significant finding is identified (including, but not limited to, changes in QT/corrected QT [QTc] interval from baseline) after enrollment, the investigator will determine if the subject can continue in the study. The investigator, or qualified designee, is responsible for

determining if any change in subject management is needed, and must document his/her review of the ECG printed at the time of collection. Any new clinically relevant finding should be reported as an AE.

9.4.4. *Tuberculosis Testing*

Subjects will be tested as indicated in the Schedule of Activities (Section 2) for evidence of active or latent TB using the QuantiFERON-TB Gold test. If the test is indeterminate, 1 retest is allowed. If the retest is indeterminate, then the subject is excluded from the study.

Subjects who have had household contact with a person with active TB must be excluded unless appropriate and documented prophylaxis for TB has been given.

Subjects with any history of **active** TB are excluded from the study, regardless of previous or current TB treatments.

9.4.5. *Safety Monitoring*

The Lilly clinical pharmacologist or clinical research physician/scientist will monitor safety data throughout the course of the study.

Lilly will review SAEs within time frames mandated by company procedures. The Lilly clinical pharmacologist or research physician will consult with the functionally independent Global Patient Safety therapeutic area physician or clinical research scientist when appropriate, and periodically review:

- trends in safety data
- laboratory analytes
- AEs including monitoring of incidence of and nature of any infections, infusion reactions, and injection site reactions.

9.4.6. *Injection / Infusion-Site Assessments*

Local tolerability at the injection or infusion site will be evaluated for erythema, induration, categorical pain, pruritus, and edema as indicated in the Section 2 and reported in the CRF. If one or more symptom(s) of an injection/infusion site reaction is reported during the assessment, a single AE for injection or infusion site reaction will be recorded on the AE page of the CRF.

In addition, pain measurements will be quantified using the the 100-mm validated Visual Analog Scale (VAS) for the subjects receiving Test SC 2 x 1 mL and the Test SC 1 x 2 mL formulation. The VAS is a well-validated tool (Williamson and Hoggart 2005) to assess injection-site pain presented as a 10-cm (100-mm) line, anchored by verbal descriptors, usually “no pain” and “worst imaginable pain.” The patient will be asked to rate any pain on a scale of 0 to 100 mm on the line immediately (within 1 minute) following the start of the injection and at time points according to the Schedule of Activities (Section 2). For the Test SC 2 x 1 mL formulation, the pain assessment will be done only for the first of the 1 mL injections.

Injection site leakage for the Test SC 1 x 2 mL and the first of the Test SC 2 x 1 mL injections will be assessed using pre-weighed filter paper, blotting the injection site immediately after the injection to absorb any post-injection leakage and placing the filter paper back on the tared analytical balance in a similar manner as previously described (Ignaut and Fu 2012). For the Test SC 2 x 1 mL formulation, the leakage assessment will be done only for the first of the 1 mL injections. The amount of leakage will be calculated by subtracting the pre-weighed filter paper measurement from the post-injection site blot filter paper measurement. Any bleeding from the injection site will also be documented.

9.4.7. Immunogenicity Assessments

Blood samples for immunogenicity testing will be collected to determine antibody production against the investigational product as specified in the Schedule of Activities (Section 2).

A risk-based approach will be used to monitor subjects who develop TE-ADAs during and following treatment with LY3074828. TE-ADAs are defined as either 2-fold increase in titer (i.e. 1:20) above the minimum required dilution (1:10) if no ADAs were detected at baseline or a 4-fold or greater increase in titer over baseline for subjects that are ADA positive at baseline. LY3074828 is a monoclonal antibody that binds to p19 of IL-23, and there is no unique/non-redundant endogenous protein counterpart, greatly minimizing the risk of cross-reactive ADA. Any potential risks of ADA development following this single dose trial would be dependent on LY3074828 exposure outside of this clinical trial. The largest potential risk would be reaction upon subsequent drug exposure that could range in severity from mild local injection site reactions to systemic anaphylaxis and/or systemic immune complex disease (Arthus-reaction). These potential risks would likely be associated with higher serum concentrations of ADA.

Given that the subjects have only a single exposure to LY3074828, any ADA response is anticipated to peak and then diminish due to lack of additional exposures. Subjects will have ADA sampling at baseline, Day 15, Day 29, Day 85, and at follow-up. Subjects that are observed to have significant (i.e. greater than 1:1000 titer) and non-decreasing titers that meet the definition of TE-ADA, will be requested to return every 3 months after the last sample to have follow-up ADA samples tested until the titer has returned to within 1 titer of their baseline or is clearly trending back to the baseline titer. The rationale for the definitions of both TE-ADA and return to baseline is based on the premise that a 1-titer change may result from expected assay variability.

Subjects followed for at least 1 year since last dose who have not returned to baseline, as defined above, will be assessed for safety concerns and, if no clinical sequelae are recognized by the clinical team, no further follow-up will be required. Subjects who have clinical sequelae that are considered potentially related to the presence of TE-ADA may also be asked to return for additional follow-up testing.

Additional samples may be collected if there is a possibility that an AE is immunologically mediated. Immunogenicity will be assessed by a validated assay designed to detect ADAs in the presence of the investigational product. Antibodies may be further characterized and/or evaluated for their ability to neutralize the activity of the investigational product.

Samples will be retained for a maximum of 15 years after the last subject visit, or for a shorter period if local regulations and ethics committee (EC) allow, at a facility selected by the sponsor. The duration allows the sponsor to respond to future regulatory requests related to the investigational product. Any samples remaining after 15 years will be destroyed.

9.5. Pharmacokinetics

At the visits and times specified in the Schedule of Activities (Section 2), venous blood samples will be collected to determine the serum concentrations of LY3074828. A maximum of 3 samples may be collected at additional time points during the study if warranted and agreed upon between both the investigator and sponsor. Instructions for the collection and handling of blood samples will be provided by the sponsor. The actual date and time (24-hour clock time) of each sampling will be recorded.

9.5.1. Bioanalysis

Samples will be analyzed at a laboratory approved by the sponsor and stored at a facility designated by the sponsor.

Concentrations of LY3074828 will be assayed using a validated enzyme-linked immunosorbent assay (ELISA).

Bioanalytical samples collected to measure investigational product concentrations will be retained for a maximum of 1 year following last subject visit for the study.

9.6. Pharmacodynamics

Not applicable.

9.7. Genetics

A blood sample will be collected for pharmacogenetic analysis as specified in the Schedule of Activities (Section 2), where local regulations allow.

Samples will not be used to conduct unspecified disease or population genetic research either now or in the future. Samples will be used to investigate variable response to LY3074828 and to investigate genetic variants thought to play a role in autoimmune and inflammatory diseases. Assessment of variable response may include evaluation of AEs or differences in efficacy.

All samples will be coded with the subject number. These samples and any data generated can be linked back to the subject only by the investigative site personnel.

Samples will be retained for a maximum of 15 years after the last subject visit, or for a shorter period if local regulations and/or EC impose shorter time limits, for the study at a facility selected by Lilly or its designee. This retention period enables use of new technologies, response to regulatory questions, and investigation of variable response that may not be observed until later in the development of LY3074828 or after it is commercially available.

Molecular technologies are expected to improve during the 15 year storage period and therefore cannot be specifically named. However, existing approaches include whole genome or exome

sequencing, genome wide association studies, multiplex assays, and candidate gene studies. Regardless of technology utilized, data generated will be used only for the specific research scope described in this section.

9.8. Biomarkers

This section is not applicable for this study.

9.9. Health Economics

This section is not applicable for this study.

10. Statistical Considerations and Data Analysis

10.1. Sample Size Determination

A total of 72 subjects will be enrolled to ensure that approximately 64 subjects complete the study (16 completers per treatment). The estimated total variability (coefficient of variation) in AUC from time zero to infinity (AUC[0-∞]), AUC from time zero to time t , where t is the last sample with a measurable concentration (AUC[0- t_{last}]), and maximum observed drug concentration (C_{max}) was 49%, 49%, and 23%, respectively, in Study AMAA following a single SC dose of 120 mg LY3074828. The coefficient of variation of 49% was used for precision estimates and is assumed for all treatment arms. A sample size of 64 subjects will provide a precision of approximately 28% for the geometric means ratio in AUC(0-∞), AUC(0- t_{last}), and C_{max} of reference to test in log scale. That is, there is a 90% probability that the half-length of the 90% confidence interval (CI) of the geometric means ratio in log scale is not larger than 28%.

Subjects who are randomized but not administered treatment may be replaced to ensure that approximately 64 subjects may complete the study.

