5.1. Overall Design

Study AMAL is a single-center, randomized, parallel-treatment, open-label, Phase 1 single-dose administration study evaluating LY3074828 in 72 healthy subjects.

Screening Period (≤ 4 weeks): Subjects will be evaluated for study eligibility ≤ 28 days prior to enrollment.

Residential Period (2 days): Subjects who fulfill the eligibility criteria will be randomized to 1 of 4 treatments, with 18 subjects randomized to each treatment, as shown below:

- **Reference:** 250 mg LY3074828; lyophilized reference formulation with $2 \times 1\text{-mL} + 1 \times 1.5\text{-mL}$ SC injections;
- **Test SC $2 \times 1\text{-mL}$:** 250 mg LY3074828; test formulation with $2 \times 1\text{-mL}$ SC injections;
- **Test SC $1 \times 2\text{-mL}$:** 250 mg LY3074828; test formulation with $1 \times 2\text{-mL}$ SC injection;
- **Test IV:** 250 mg LY3074828; test formulation by IV infusion over at least 30 minutes.

Subjects will report to the clinical research unit (CRU) on Day -1 and remain at the CRU until after the scheduled procedures have been completed on Day 2 as defined in the Schedule of Activities (Section 2). After randomization, study drug will be administered by either IV infusion or SC injection in the morning of Day 1 after an overnight fast. Subjects within the same enrollment group may be dosed across several days if required by the site for logistical or other purposes.

Outpatient Follow-up Period (approximately 14 weeks): The follow-up period will include outpatient visits for a total of 12 weeks following Day 1 dose administration to assess tolerability and PK of LY3074828. An end-of-study follow-up visit will be scheduled within 7 to 14 days after the last procedure or upon early discontinuation (ED).

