5.4. Scientific Rationale for Study Design

Single doses of 250 mg LY3074828 and the PK sampling timepoints have been selected to generate PK profiles sufficient to fulfill the study objectives.

As the primary endpoints are PK-related and therefore considered to be objective in nature, it is not considered appropriate to include a placebo control during this study. Furthermore, the secondary objective relating to tolerability is a comparison between formulations and therefore addition of a placebo control will not contribute to the scientific validity of the study. As only a single dose level (250 mg) of LY3074828 will be administered during this study, and subjects and site staff will be aware of the administration route (eg, number of SC injections, IV dosing), an unblinded study design has been selected.

Due to the maximum achievable concentration of the lyophilized reference formulation being 72 mg/mL, it is not possible to administer 250 mg with a total injection volume of 2 mL for consistency with the other SC treatments. The total injection volume for the reference formulation was therefore increased to 3.5 mL to ensure a comparable total dose to the test formulation. Although the theoretical total dose for this treatment is 252 mg, the dose levels for all treatments are referred to as 250 mg for the purposes of this protocol.

A parallel-group design was chosen because a crossover design is impractical for compounds that have long half-lives, such as monoclonal antibodies. In addition, a crossover study design could confound PK data if subjects develop neutralizing anti-drug antibodies (ADAs).

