7. SAMPLE SIZE JUSTIFICATION

A total of 72 subjects will be enrolled to ensure that approximately 64 subjects complete the study (16 completers per treatment). The estimated total variability (coefficient of variation) in AUC from time zero to infinity ($AUC[0-\infty]$), AUC from time zero to time t , where t is the last sample with a measurable concentration ($AUC[0-t_{last}]$), and maximum observed drug concentration (C_{max}) was 49%, 49%, and 23%, respectively, in Study AMAA following a single SC dose of 120 mg LY3074828. The coefficient of variation of 49% was used for precision estimates and is assumed for all treatment arms. A sample size of 64 subjects will provide a precision of approximately 28% for the geometric means ratio in $AUC(0 -\infty)$, $AUC(0-t_{last})$, and C_{max} of reference to test in log scale. That is, there is a 90% probability that the half-length of the 90% confidence interval (CI) of the geometric means ratio in log scale is not larger than 28%.

Subjects who are randomized but not administered treatment may be replaced to ensure that approximately 64 subjects may complete the study.

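### With 64 completers and a CV of 49%, the probability that the 90% CI half-length is at most 28% is about 55–62%, not the stated 90%

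*Protocol*

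**What the plan says.** Protocol section 10.1 sets the size of the trial: "A total of 72 subjects will be enrolled to ensure that approximately 64 subjects complete the study (16 completers per treatment"). It takes CVs of 49% for both AUC measures and 23% for Cmax from Study AMAA, and then uses the larger value throughout: "The coefficient of variation of 49% was used for precision estimates and is assumed for all treatment arms".

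The precision claim follows: "A sample size of 64 subjects will provide a precision of approximately 28% for the geometric means ratio" of reference to test, on the log scale, for both AUCs and Cmax. The next sentence defines what this means, with 28% as the bound: "there is a 90% probability that the half-length of the 90% confidence interval (CI) of the geometric means ratio in log scale is not larger". SAP section 7 carries the same statement ("there is a 90% probability that the half-length of the 90% confidence interval (CI").

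Protocol section 5.1 describes equal allocation, with subjects "randomized to 1 of 4 treatments, with 18 subjects randomized to each treatment". SAP section 9.3.2 specifies one linear model with contrasts for the comparisons. Protocol section 10.3.2.2 asks for a single model where possible.

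**The concern.** The half-length of a confidence interval is itself random, because it depends on the SD estimated from the trial data. A statement that it stays below a bound with 90% probability must allow for that. The 28% figure agrees with the half-length obtained by inserting the planning SD as if it were known. That leaves a chance only somewhat better than even of achieving 28% or less.

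The protocol and SAP give no power calculation and no equivalence margin, so this sentence is the only quantitative support for 16 completers per arm. It bears on the primary comparison, because the AUCs are the primary parameters and the 49% CV is their own. The interim results are meant to trigger manufacturing work and a formal bridging study and to inform Phase 3 dose selection. Those planning around them should know how wide the intervals are likely to be.

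**Working it through.** **Inputs, all from the documents**

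- Completers: 16 per arm, 64 in total (protocol 10.1).
- CV: 49% in every arm (protocol 10.1). The design is parallel-group (protocol 5.4), so total between-subject variability applies.
- Interval: two-sided 90% CI for the log ratio, target half-length 0.28, assurance 90% (protocol 10.1).
- Comparison: Test SC 2 × 1-mL against Reference, 16 versus 16.
- Error degrees of freedom: 4 × 15 = 60 for the SAP's single four-arm model; 2 × 15 = 30 for a model with only the two compared arms.

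**Step 1: reproduce 28%**

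- Log-scale SD: σ = √ln(1 + 0.49²) = √ln(1.2401) = 0.4639.
- Standard error of the log ratio: 0.4639 × √(2/16) = 0.1640.
- Half-length with the SD at its planning value, h = t(0.95, df) × SE:
  - 60 df: 1.6706 × 0.1640 = 0.274
  - 30 df: 1.6973 × 0.1640 = 0.278

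This matches the plan's figure of approximately 28%, but no 90% probability has entered the calculation yet.

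**Step 2: add the 90% assurance**

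The estimated variance follows a scaled chi-square distribution, so the 90th percentile of the half-length is h × √(χ²(0.90, df)/df).

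- 60 df: 0.274 × √(74.40/60) = 0.274 × 1.1135 = 0.305
- 30 df: 0.278 × √(40.26/30) = 0.278 × 1.1584 = 0.322 (0.3225 before rounding h)

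**Step 3: the probability actually attached to 28%**

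P(half-length ≤ 0.28) = P(χ² on df ≤ df × (0.28/h)²).

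- 60 df: P(χ² ≤ 62.66) = 0.618
- 30 df: P(χ² ≤ 30.35) = 0.552

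A simulation of 200,000 trials gave 0.617 and 0.554, 90th percentiles of 0.305 and 0.323, and mean half-lengths of 0.273 and 0.276.

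**Step 4: the ratio scale**

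Around an observed ratio of 1, a half-length of 0.28 gives 0.76 to 1.32. The 90%-assured half-lengths give 0.74 to 1.36 (60 df) and 0.72 to 1.38 (30 df).

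**Step 5: other readings of the sentence**

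| Reading | 90%-assured half-length | P(≤ 0.28) |
|---|---|---|
| Normal quantile instead of t, 16 per arm | 0.300–0.313 | 0.65–0.68 |
| 0.49 used directly as the log SD | 0.322–0.341 | 0.38–0.39 |
| Three SC arms in the model, 45 df | 0.311 | 0.59 |
| All 72 complete, 18 per arm, 68 df | 0.285 | 0.85 |
| Pooled SC (32) versus IV (16), 60 df | 0.264 | 0.98 |

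- Reading approximately 28% as anything up to 28.5% raises the probability to 0.61 (30 df) or 0.69 (60 df).
- The pooled SC versus IV contrast meets the claim, but the sentence concerns reference to test.
- On the ratio scale, 1 − exp(−0.3225) = 27.6%, but the text specifies the log scale.

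**Step 6: what would make the sentence true**

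- Completers per arm for 28% with 90% assurance: 19 under the four-arm model (assured half-length 0.277) or 21 with two arms (0.274).
- Alternatively, at 16 per arm the CV would have to be about 45% (60 df) or 42% (30 df).

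**The case against.** The arithmetic is not open to serious dispute. The case on the other side is that it matters little.

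- **No decision depends on interval width.** The plan reports ratios with 90% CIs and has no margin, test or go/no-go rule tied to a half-length. Readers of the results will see the actual intervals. This stands: no analysis or estimate changes.
- **The planned analysis is the four-arm model.** The relevant figures are then 62% and 30.5%, a gap of 2.5 points on the log scale. This also stands; the 55% and 32% figures apply only if the model is restricted to the two compared arms.
- **The analysed number may exceed 16 per arm.** The PK population is every dosed subject with evaluable data, and 72 are enrolled. The assured half-length is 0.295 at 17 per arm and 0.285 at 18 per arm. This narrows the practical shortfall, but the sentence refers to 64 subjects, and the claim still fails with all 72.
- **Cmax is covered by the same sentence.** At its own CV of 23%, the 28% bound is met with probability close to 1 (assured half-length 0.149 or 0.158). This is correct, but it does not help the AUCs, which are the primary parameters.

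These points limit the consequence. None of them makes the stated 90% correct.

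**Conclusion.** The concern holds. On the plan's own inputs, the stated 90% probability is 62% under the single model the SAP specifies, or 55% with the two compared arms alone. The half-length that can be promised with 90% probability is about 31% or 32%, not 28%.

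This rests on log-normal PK parameters, a common CV of 49% that is the true value, and 16 analysed subjects per arm. The first follows from the planned log-scale analysis, and the other two are the plan's own assumptions. The effect is a moderate overstatement of precision in the trial's only sample-size justification. It is not a loss of power, and it does not invalidate the planned analysis.

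**What to change.** Correct the precision statement in protocol section 10.1 and SAP section 7, using one model throughout. Under the SAP's four-arm model it could read:

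*With 64 completers (16 per arm), a CV of 49% and a pooled four-arm variance, the expected half-length of the 90% CI for the log ratio is about 27%, and there is a 90% probability that it will not exceed about 31%.*

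If only the two compared arms are to be modelled, the corresponding figures are about 28% and 32%.

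A separate Cmax figure is optional. At a CV of 23% the half-length is about 13% expected and 15% with 90% probability (four-arm), or 14% and 16% (two-arm).

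The cost is wording only, with a slightly less favourable stated precision. No subjects are added and the design and analysis are unchanged. Keeping 28% with 90% assurance would instead need 19 completers per arm (76 in total) under the four-arm model, which is more than the 72 to be enrolled.
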